10.6. Publication Policy

By signing the study Protocol, the investigator and his or her institution agree that the results of the study may be used by the sponsor, Incyte Corporation (Incyte), for the purposes of national and international registration, publication, and information for medical and pharmaceutical professionals. Study results will be published in accordance with applicable local and national regulations. If necessary, the authorities will be notified of the investigator's name, address, qualifications, and extent of involvement. The terms regarding the publication of study results are contained in the agreement signed with the sponsor or its designee. A signed agreement will be retained by the sponsor or its designee.

APPENDIX A. INFORMATION REGARDING EFFECTIVENESS OF CONTRACEPTIVE METHODS

For Subjects Participating in the Study:

The following methods that can achieve a failure rate of less than 1% per year when used consistently and correctly are considered as highly effective birth control methods. Such methods include:

- Combined (estrogen and progestogen containing) hormonal contraception associated with inhibition of ovulation¹
 - oral
 - intravaginal
 - transdermal
- Progestogen-only hormonal contraception associated with inhibition of ovulation¹
 - oral
 - injectable
 - implantable²
- Intrauterine device (IUD)²
- Intrauterine hormone-releasing system (IUS)²
- Bilateral tubal occlusion²
- Vasectomised partner^{2,3}
- Sexual abstinence⁴

Acceptable birth control methods that result in a failure rate of more than 1% per year include:

- progestogen-only oral hormonal contraception, where inhibition of ovulation is not the primary mode of action
- male or female condom with or without spermicide⁵
- cap, diaphragm or sponge with spermicide⁵

¹ Hormonal contraception may be susceptible to interaction with the IMP, which may reduce the efficacy of the contraception method.

² Contraception methods that in the context of this guidance are considered to have low user dependency.

³ Vasectomised partner is a highly effective method provided of avoiding pregnancy that partner is the sole sexual partner of the WOCBP trial participant and that the vasectomised partner has received medical assessment of the surgical success.

⁴ In the context of this guidance, sexual abstinence is considered a highly effective method only if defined as refraining from heterosexual intercourse during the entire period of risk associated with the study treatments. The reliability of sexual abstinence needs to be evaluated in relation to the duration of the clinical trial and the preferred and usual lifestyle of the subject.

⁵ A combination of male condom with either cap, diaphragm or sponge with spermicide (double barrier methods) are also considered acceptable, but not highly effective, birth control methods.

Source: [CTFG 2014](#).

APPENDIX B. POTENT CYP3A4 INHIBITORS AND FLUCONAZOLE

In clinical studies with CYP3A4 inhibitors, elevated levels of INCB018424 of approximately 2-fold have been observed after oral administration. Additionally, simulations using physiologically based PK models suggested that fluconazole (a dual CYP3A4 and CYP2C9 inhibitor) increases steady-state ruxolitinib AUC by approximately 1- to 3-fold after oral administration. Thus, these concomitant medications should not be taken by subjects beginning 2 weeks or 5 half-lives (whichever is longer) before the first application of study drug until the last administration (either Week 24 or Week 52; however, topical use of these agents if the systemic bioavailability is low may be permitted on a case-by-case basis. The following is a list of potent CYP3A4 inhibitors and fluconazole. The sponsor should be contacted with any questions regarding concomitant medications that might be considered potent CYP3A4 inhibitors but are not on this list.

- boceprevir
- clarithromycin
- cobicistat
- conivaptan
- danoprevir
- elvitegravir
- fluconazole
- grapefruit juice
- idelalisib
- indinavir
- itraconazole
- ketoconazole
- LCL161
- lopinavir
- mibefradil
- nefazodone
- nelfinavir
- posaconazole
- ritonavir
- saquinavir
- telaprevir
- telithromycin
- tipranavir
- troleandomycin
- voriconazole

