12. Subjects taking potent systemic CYP3A4 inhibitors or fluconazole within 2 weeks or 5 half-lives, whichever is longer, before the baseline visit (topical agents with limited systemic availability are permitted, see [Appendix B](#)).
13. Subjects who have previously received JAK inhibitor therapy, systemic or topical (eg, ruxolitinib, tofacitinib, baricitinib, filgotinib, lestaurtinib, pacritinib).
14. Women who were pregnant during the 12 months before screening.
15. Women who are breastfeeding.
16. Current or recent history (< 30 days before screening and/or < 45 days before randomization) of a clinically meaningful bacterial, fungal, parasitic, or mycobacterial infection.
17. History of unstable ischemic heart disease (including percutaneous cardiac intervention, myocardial infarction, or anginal acceleration within the past 6 months) or uncontrolled hypertension (blood pressure > 150/90 mmHg on at least 2 subsequent readings).
18. History of alcoholism or drug addiction within 1 year before screening, or current alcohol or drug use that, in the opinion of the investigator, will interfere with the subject's ability to comply with the administration schedule and study assessments.
19. Current treatment or treatment within 30 days or 5 half-lives (whichever is longer) before the baseline visit with another investigational medication or current enrollment in another investigational drug protocol.
20. Use of any prohibited medications (see Section [5.6.3](#)) within 14 days or 5 half-lives (whichever is longer) of the baseline visit.
21. Donation of blood within 6 weeks before screening or of plasma within 2 weeks before screening and unwillingness to forego further blood product donation during the study.
22. Receipt of blood products within 2 months before screening.
23. Subjects with a history of malignancy, except for the following adequately treated, nonmetastatic malignancies: basal cell skin cancer not involving areas with vitiligo, squamous cell carcinomas of the skin not involving areas with vitiligo, or *in situ* cervical cancer.
24. Subjects who anticipate receiving a live or live-attenuated vaccination from screening through the final follow-up visit.
25. Subjects with known allergy or reaction to any component of the study formulation.
26. Subjects who, in the opinion of the investigator, are unable or unlikely to comply with the administration schedule and study evaluations.

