4. INVESTIGATIONAL PLAN

4.1. Overall Study Design

This is a 3-part, randomized, double-blind, and vehicle-controlled study in subjects with vitiligo who have depigmented areas including at least 0.5% of the total BSA on the face and at least 3% of the total BSA on nonfacial areas as determined by the palmar or handprint (palm plus 5 digits) method. Approximately 150 subjects, aged 18 to 75 years, will be randomized to 1 of 4 dose strengths of INCB018424 cream (1.5% BID, 1.5% QD, 0.5% QD, 0.15% QD) or vehicle in a 1:1:1:1 ratio and stratified by age (≤ 30 or > 30 years).

Subjects will receive blinded treatment for up to 52 weeks to examine efficacy, safety, and tolerability. The 3 parts of the study include a 24-week, double-blind, vehicle-controlled treatment period; a 28-week, continued, double-blind treatment period; and a 104-week, open-label extension period (see [Figure 1](#)). The primary endpoint of F-VASI50 will be evaluated at Week 24. After completion of the Week 24 assessments, subjects randomized to vehicle will be randomized to 1 of the 3 higher active treatment groups in a 1:1:1 ratio while maintaining the blind. Subjects in the 0.15% QD dose group who do not achieve a $\geq 25\%$ improvement from baseline on F-VASI (nonresponders of F-VASI25) will be re-randomized to 1 of the 3 higher active treatment groups while maintaining the blind. Subjects randomized to INCB018424 0.15% QD who achieve a $\geq 25\%$ improvement from baseline on F-VASI will remain on the same dose until Week 52. Subjects randomized to INCB018424 1.5% BID, 1.5% QD, and 0.5% QD will remain on the same dose until Week 52.

At any time during the study, if a subject has expansion of existing areas of depigmentation or development of new areas of depigmentation, then after a visit to document the VASI score and other measures of vitiligo, subjects are to apply study drug to those areas that are new or expanded since baseline in addition to areas treated since baseline as long as the total BSA to be treated does not exceed 20%. This visit may be unscheduled.

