After completion of the Week 52 assessments, subjects who continue to be eligible for the study will be offered the opportunity to receive an additional 104 weeks of open-label treatment with INCB018424 1.5% cream BID. To be eligible, subjects must have completed the baseline, Week 24, and Week 52 visit assessments, be compliant with study medication, have no clinically significant changes in laboratory parameters from baseline (must meet entry criteria regarding cytopenias and liver assessments) and, in the opinion of the investigator, have no safety concerns regarding the previous 52 weeks of treatment with INCB018424 cream. In the open-label extension, subjects may be offered low-dose narrow band-UVB phototherapy in addition to INCB018424 cream in consultation with the investigator and sponsor.

[figure not shown]
Subjects who are eligible for the open-label extension who have complete facial repigmentation (F-PhGVA score of 0) may stop applying study drug to the face, decrease the application rate to QD, or continue BID based on investigator judgement at Weeks 52 and 80 (after Week 80, subjects may also be permitted to modify their treatment regimen after the investigator has consulted with the sponsor). Subjects may continue to apply INCB018424 1.5% QD or BID to areas of vitiligo on the body; dose will be determined by the investigator based on level of repigmentation. A subject who had decreased the dose to QD or stopped applying INCB018424

to the face who has a loss of pigmentation on the face (F-PhGVA of at least 1) may increase the dose from QD to BID or restart application of INCB018424 1.5% BID after a visit to document the F-VASI score and other measures of vitiligo.

Sites will remain blinded to study drug, but some personnel at Incyte without direct contact with sites will be unblinded for the interim analyses. This internal committee will be charged with evaluating the unblinded interim analysis results (when at least 50% subjects first have Week 12 and then Week 24 data available). As full repigmentation is anticipated to be a slow process, the interim analysis results will determine preliminary efficacy of the treatment groups for future study and planning. After Week 24, the members of the primary endpoint assessment team from Incyte will be unblinded.

If any other skin products that are permitted under the study Protocol are used, subjects should continue these unchanged during the study.

Figure 1: Study Design Schema

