| Patient - PaGVA (face and total body) | 7.6.5 | | | X | | X | | X |
| PaGIC-V | 7.6.6 | | | X | | X | | X |

^a Urinalysis and 12-lead ECG to be conducted at the EOT visit (Week 52, Week 156, or early discontinuation).

^b All women will have a urine pregnancy test conducted at all visits in this portion of the study.

Table 4: Schedule of Assessments for the Open-Label Extension Period (Weeks 52 Through 156)

| Evaluation | Section | Open-Label Extension Period | | | | | | | Follow-Up | |
|--|---------|-----------------------------|------------------|------------------|------------------|------------------------------|---------------------------------|-----------------------------|----------------------------|-------------------------|
| | | Week 52 ± 7 d | Week 56 ± 7 d | Week 68 ± 7 d | Week 80 ± 7 d | Weeks 92 and 104 ± 7 d | Weeks 116, 128, 140 ± 7 d | Week 156 ET/EOT ± 7 d | Months 1 and 3 ± 7 d | Month 6 EOS ± 7 d |
| Administrative procedures | | | | | | | | | | |
| Contact IRT | 7.2 | | X | X | X | X | X | X | X | X |
| Prior/concomitant medications | 7.4 | | X | X | X | X | X | X | X | X |
| Apply study drug | 5.2 | X | X | X | X | X | X | | | |
| Study drug and diary card dispensed | 7.10.1 | X | X | X | X | X | X | | | |
| Collect study drug tubes; collect and review diary cards | 5.3 | | X | X | X | X | X | X | | |
| Assess compliance | 5.3 | | X | X | X | X | X | X | | |
| Safety procedures/assessments | | | | | | | | | | |
| Comprehensive physical examination | 7.5.2.1 | | | | | | | X | | |
| Targeted physical examination | 7.5.2.2 | | X | X | X | X | X | | X | X |
| Vital signs | 7.5.3 | | X | X | X | X | X | X | X | X |
| Hematology and chemistry assessments | 7.5.5 | | X | X | X | X | X | X | X | X |
| Urinalysis | 7.5.5.3 | | | | | | | X | | |
| Pregnancy test ^a | 7.5.5.4 | | X | X | X | X | X | X | X | X |
| 12-lead ECG | 7.5.4 | | | | | | | X | | |
| Assess AEs | 7.5.1 | | X | X | X | X | X | X | X | X |
| Efficacy and other assessments | | | | | | | | | | |
| VASI (face and total body) | 7.6.1 | | X | X | X | X | X | X | X | X |
| BSA (face and total body) | 7.6.2 | | X | X | X | X | X | X | X | X |
| VETF | 7.6.3 | | X | X | X | X | | | | |
| Physician - PhGVA (face and total body) | 7.6.4 | | | X | X | X | X | X | | X |
| Patient - PaGVA (face and total body) | 7.6.5 | | | X | X | X | X | X | | X |
| PaGIC-V | 7.6.6 | | | X | X | X | X | X | | X |

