7.5.4. Electrocardiograms

All 12-lead ECGs will be performed with the subject in a recumbent or semirecumbent position after 5 minutes of rest.

Interpretation of the 12-lead ECG will be used to determine eligibility at screening. An additional ECG will be performed at the EOT visit (Week 52, Week 156, or if the subject discontinues treatment). Throughout the study, a 12-lead ECG may be conducted if associated with an AE or other signs or symptoms.

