7.5.5.3. Urinalysis

Urinalysis will be performed by a central laboratory at screening and EOT (Week 52, Week 156, or if the subject discontinues treatment, see [Table 2](#), [Table 3](#), and [Table 4](#)).

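### Appendix B ends the CYP3A4 inhibitor and fluconazole restriction at Week 24 or Week 52, although treatment can run to Week 156

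*Protocol*

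**What the plan says.** Appendix B of the protocol restricts potent CYP3A4 inhibitors and fluconazole because they raise ruxolitinib levels after oral dosing. The restriction starts 2 weeks or 5 half-lives, whichever is longer, "before the first application of study drug until the last administration (either Week 24 or Week 52".

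Elsewhere the protocol describes end of treatment differently:

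- Table 3, footnote a (Section 6), on urinalysis and ECG: "to be conducted at the EOT visit (Week 52, Week 156, or early discontinuation".
- Section 7.5.4: "An additional ECG will be performed at the EOT visit (Week 52, Week 156, or if the subject discontinues treatment".
- Section 7.5.5.3: "Urinalysis will be performed by a central laboratory at screening and EOT (Week 52, Week 156, or if the subject discontinues treatment".

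Section 4.1 sets out who is treated and for how long. For the three higher-dose arms, "Subjects randomized to INCB018424 1.5% BID, 1.5% QD, and 0.5% QD will remain on the same dose until Week 52". After Week 52, eligible subjects "will be offered the opportunity to receive an additional 104 weeks of open-label treatment with INCB018424 1.5% cream BID".

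Exclusion criterion 20 in Section 3.2 points to a separate section for prohibited drugs: "Use of any prohibited medications (see Section" 5.6.3). That section is not visible in the public copy.

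**The concern.** The parenthesis in Appendix B tells the site which weeks count as the last administration, and those weeks are wrong for this design. A site could reasonably take the restriction to end at Week 52 for a subject who is still applying 1.5% cream twice daily.

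The restriction is a safety rule, and its reason, higher drug levels with these inhibitors, holds for as long as study drug is applied. Every subject entering the extension is offered 1.5% BID, the highest regimen in the study. In the visible text, Appendix B is also the only specific rule on these drugs during treatment. Exclusion criterion 12 covers only the time before baseline. Section 5.6 asks only that concomitant medications stay stable if possible. The extension eligibility conditions in Section 4.1 do not mention CYP3A4 inhibitors.

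The stake is consistent safety handling in the open-label period, not the efficacy conclusions.

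**Working it through.** **1. Reproduce the protocol's own timeline.** Section 4.4 gives 4 weeks of screening, 24 weeks of vehicle-controlled treatment, 28 weeks of continued double-blind treatment, an optional 104-week extension and 24 weeks of follow-up, for a total of up to 184 weeks.

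- Treatment: 24 + 28 + 104 = 156 weeks.
- Participation: 4 + 156 + 24 = 184 weeks, as stated.

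The planned end of treatment is therefore Week 52 for a subject who does not enter the extension and Week 156 for one who completes it. Tables 3 and 4 carry the end-of-treatment label at exactly those two visits. Table 2 does not label Week 24 that way.

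**2. Is Week 24 a planned last dose for anyone?** From Section 4.1:

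| Group at Week 24 | Planned treatment after Week 24 |
|---|---|
| 1.5% BID, 1.5% QD, 0.5% QD | Same dose to Week 52 |
| Vehicle | Re-randomized to one of the three higher active regimens |
| 0.15% QD, F-VASI improvement of at least 25% | Same dose to Week 52 |
| 0.15% QD, F-VASI improvement below 25% | Re-randomized to one of the three higher active regimens |

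Every group continues on active drug. A subject may stop at Week 24, but that is early discontinuation, not a scheduled end.

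**3. Compare the end points.**

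| Source in the protocol | Scheduled end of treatment |
|---|---|
| Appendix B | Week 24 or Week 52 |
| Table 3 footnote a; Sections 7.5.4 and 7.5.5.3 | Week 52 or Week 156 (or discontinuation) |

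Only Week 52 is common to both. Appendix B names one week that is not a planned end and omits one that is.

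**4. Size of the gap if the parenthesis is followed literally.** Gap = actual last week of treatment − 52, the latest week named in Appendix B.

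- Subject who stops at Week 52: 52 − 52 = 0 weeks.
- Subject who completes the extension: 156 − 52 = 104 weeks, which is 104/156 = 67% of the longest possible treatment period.

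**5. What would pick up use in that gap.** Table 4 schedules concomitant medication review, adverse events, hematology and chemistry at Weeks 56, 68, 80, 92, 104, 116, 128, 140 and 156, which is nine visits. Use would be recorded, but only after it had happened.

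**The case against.** The strongest reply is that the rule itself is right. It runs to the last administration, which for an extension subject is the last open-label dose, and the weeks in brackets only illustrate it. Harm requires a site to let the illustration override the rule for a subject to whom it is still dispensing drug. This stands as a limit on the point: the text is inconsistent and does not clearly permit these drugs after Week 52. It does not remove the inconsistency, since the brackets say which weeks are meant and a site could follow either half.

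Second, Section 5.6.3 may state the restriction correctly, and text missing from the public copy cannot be counted as absent from the plan. That also stands, so no gap in the full protocol's safety handling can be shown. A correct Section 5.6.3 would still conflict with Appendix B, so Appendix B needs the correction either way.

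Third, other safeguards exist: mandatory interruption for specified laboratory abnormalities and Grade 3 or 4 drug-related events (Section 5.4.2), renewed cytopenia and liver criteria at extension entry (Section 4.1), and a 20% cap on treated body surface area. They limit the consequences of a misreading. The interruption rules, however, act only once toxicity has appeared, and none of these measures corrects a wrong end date.

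Fourth, no risk has been quantified. Appendix B's figures, about 2-fold for CYP3A4 inhibitors and about 1- to 3-fold for fluconazole from simulation, are for oral dosing. This is correct, and the size of any effect with the cream is unknown.

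Finally, the three end-of-treatment statements concern ECG and urinalysis timing, not medication. That is true, but they do fix when treatment ends, which is the event that Appendix B refers to.

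**Conclusion.** The concern holds. The weeks in Appendix B do not match the Version 3 design: Week 24 is no arm's planned last dose, and Week 156 is left out. Read literally, the parenthesis would end a safety restriction 0 to 104 weeks before dosing stops. The upper figure assumes a subject who completes the optional extension and a site that follows the brackets over the words before them. It measures calendar time, not risk or the number of subjects affected.

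Confidence in the wording mismatch is high. Whether any site was misled, and whether Section 5.6.3 already states the rule properly, cannot be determined from the public documents. Sample size, power, type I error and the Week 24 and Week 52 analyses are untouched. It should be corrected because it sits in an operative safety instruction and costs almost nothing to put right.

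**What to change.** In Appendix B, either delete the parenthesis, so that the restriction simply runs to the last administration, or replace its contents with the three end points already used in Table 3 footnote a: Week 52, Week 156 or early discontinuation. Then confirm that Section 5.6.3 gives the same end point. The cost is one line of protocol wording, with no change to procedures, visits or analyses.

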APPENDIX C. VITILIGO AREA SEVERITY INDEX

VASI Score range (0 - 100). Degree of depigmentation scale:

- 1.00 (100%) - Complete depigmentation, no pigment is present.
- 0.90 (90%) - Specks of pigment present.
- 0.75 (75%) - Depigmented area exceeds the pigmented area.
- 0.50 (50%) - Pigmented and depigmented areas are equal.
- 0.25 (25%) - Pigmented area exceeds depigmented area.
- 0.10 (10%) - Only specks of depigmentation present.
- 0.0 (0%) - No depigmentation present.

| | A | B | A*B |
|------------------------|-----------------------------------|-----------------------------|-----------------------|
| Location | Area involved (in hand prints) | Degree of depigmentation | Total Handprint Units |
| Hands | | | |
| Upper extremities | | | |
| Trunk | | | |
| Lower extremities | | | |
| Feet | | | |
| Head/Neck | | | |
| Body Total VASI | | | 0-100 |

A handprint unit (palm + 5 digits) is equal to 1% of the BSA.

APPENDIX D. VITILIGO EUROPEAN TASK FORCE SCALE

General Recommendations:

Hands and feet are included in evaluation of extent in arms and legs, but evaluated separately and globally for staging and spreading (ie, hands and feet must be staged separately/globally as one area). Staging and Spreading can be assessed simultaneously using a Wood's lamp. Use largest patch in each territory.

Recommendation to assess extent: The subject's palm including digits averages 1% BSA. Please draw the patches and mark the evaluated patches on figure below.

Recommendation to assess stage using Wood's lamp (with magnifying lens):

- Stage 0: normal pigmentation (no depigmentation in area graded)
- Stage 1: incomplete pigmentation (including spotty depigmentation, trichrome, and homogeneous lighter pigmentation)
- Stage 2: complete depigmentation, a few white hairs do not change stage
- Stage 3: partial hair whitening < 30%
- Stage 4: complete hair whitening

Recommendation to assess spreading:

- First look at patch limits using natural light.
- Second compare with Wood's lamp limits.

[figure not shown]
Score 0 means similar limits.

Score 1 means progressive vitiligo (ongoing subclinical depigmentation)

[figure not shown]
Score -1 means regressive vitiligo (ongoing subclinical repigmentation)

| Area | % Area | Staging* (0-4) | Spreading* (-1 +1) |
|----------------------|--------|-------------------|-----------------------|
| Head and neck (0-9%) | | | |
| Trunk (0-36%) | | | |
| Arms (0-18%) | | | |
| Legs (0-36%) | | | |
| Hands and feet | | | |
| Totals (0-100%) | | 0-20 | (-5 +5) |

*largest patch in each area

Source: [Taïeb and Picardo 2007](#).

